#### 6.6. Statistical Tests

The default significant level will be 5%; confidence intervals (CIs) will be 95% and all tests will be two-sided, unless otherwise specified in the description of the analyses.

# 6.7. Values below or Above the Quantification Limit

- ADA against efgartigimod:titer of positive ADA samples reported as "negative titer" will be imputed by 1. Listings will always present "negative titer".
- Safety and PD values expressed as below (or above) the quantification limit will be imputed by the value of the quantification limit itself. For participants with a baseline PD value below/above the quantification limit, the PD parameter will be excluded from the statistical analyses involving change and percent change from baseline. Listings will always show the non-imputed values.
- Pharmacokinetic concentrations below the lower quantification limit will be reported in the listings as BLQ. For descriptive statistical analysis, all BLQ values will be set to zero. Listings will always present BLQ.

Document: BIOSdata\argenx\Efgartigimod\HAB40220\Biostatistics\Documentation\SAP

Author: Version Number: 3.0

Version Date: 02 May 2024

Template No.: CS\_TP\_BS016 Revision 7 Reference: CS\_WI\_BS005

Page 27 of 64

### 6.8. Common Calculations

For quantitative measurements, change from baseline will be calculated as:

Change from baseline at Visit X = Value at Visit X - baseline value.

A percent change from baseline can be calculated as.

• Percent change from baseline at Visit X = (actual value at Visit X -baseline value) \*100/baseline value.

### 6.9. Software Version

All analyses will be conducted using SAS version 9.4 or higher.

# 7. STATISTICAL CONSIDERATIONS

### 7.1. Missing Data

For imputation of missing values related to efficacy and safety, see appropriate section of the applicable endpoints.

Missing efgartigimod concentrations will not be imputed.

# 7.2. Output Presentation

For continuous variables, full descriptive statistics will only be presented if there are at least 2 non-missing observations. Alternatively, only the number of non-missing data points and mean are shown. In tables by analysis visit, only analysis visits with at least 10 participants (overall) will be shown.

Descriptive statistics for safety and efficacy will include the number of non-missing data points, the arithmetic mean, the standard deviation (SD), the median, minimum, Q1, Q3, maximum, and for efficacy the standard error (SE) and 95% CI may be provided in addition (refer to output templates for details).

Mean, Q1, Q3 95% Confidence interval and median will be presented with one more decimal place than the measured values. SE and SD will be presented with two more decimal places than the measured values. Minimum and maximum will be presented with the same number of decimal places as the measured values.

Document: BIOSdata\argenx\Efgartigimod\HAB40220\Biostatistics\Documentation\SAP

Author: Version Number: 3.0

Version Date: 02 May 2024

Template No.: CS\_TP\_BS016 Revision 7 Reference: CS\_WI\_BS005

Page 28 of 64

Descriptive statistics for PD parameters will include the number of non-missing data points, the arithmetic mean, the SD, the SE, the 95% CI, the median, minimum, Q1, Q3, and maximum. Descriptive statistics of total IgG levels will be presented in  $\mu$ g/mL.

Descriptive statistics for PK serum concentrations will include the number of observed values, arithmetic mean, SD, median, minimum and maximum, CV%, the GM, and geometric CV%. Serum concentrations will be reported as received by the bioanalytical laboratory.

Descriptive statistics for PK concentrations will be presented with 3 significant digits in  $\mu g/mL$  for efgartigimod (where appropriate), except values  $\geq 1000$  which will be presented without the decimals and rounded to the nearest integer. If at least one BLQ value is reported at a specific time point, the GM and geometric CV% for that time point will not be calculated. In addition, if more than half of the values per time point are BLQ, the arithmetic mean will be reported as BLQ and SD, CV%, GM, and geometric CV% will not be calculated.

Descriptive statistics for immunogenicity titer values will include the number of observed values, arithmetic mean, SE, 95% CI, median, Q1, Q3, minimum, maximum, the GM, and geometric CV%.

For event-type safety data, the number and percentage of participants with an event will be shown. The denominator will be all participants in the analysis set per treatment.

For frequency tabulations and cross-tabulations, the denominator will be the number of participants per treatment arm. For tables where results are shown by analysis visit, the denominator will be the number of participants per treatment arm and analysis visit. Missing values will not be included in the denominator count when computing percentages. For cross-tabulation of post-baseline results versus baseline results, a "missing" category will be shown for baseline results, if applicable. Percentages will be presented with 1 decimal place.

Appendix 1 shows conventions for presentation of data in outputs.

# 7.3. Multiple Comparisons/ Multiplicity

No multiple comparison adjustment or alpha sharing to be considered.

Document: BIOSdata\argenx\Efgartigimod\HAB40220\Biostatistics\Documentation\SAP

Author: Version Number: 3.0

Version Date: 02 May 2024

Template No.: CS\_TP\_BS016 Revision 7 Reference: CS\_WI\_BS005

Effective Date: 01Nov2021

argenx Confidential 29

Page 29 of 64

### 8. DISPOSITION AND WITHDRAWALS

All participants who provide informed consent will be accounted for in this study.

### 8.1. Disposition

The number of participants will be summarized for ENR for the Final Planned Analysis (FPA). The number of participants per country and site will also be provided using the SAF for the FPA. The number of participants who completed or discontinued the treatment using the SAF, for IAWK12, IAWK24 and FPA and/or the study along with the reason for discontinuation will be summarized using the FAS for both the IAWK12, IAWK24 and FPA.

Participant disposition and withdrawals will be presented for the FAS set.

Data will be tabulated at least for;

- participants each analysis sets for the FPA.
- number and percentage of participants randomized, completed, or discontinued the study for the IAWK12, IAWK24 and FPA.
- number and percentage of participants for each study discontinuation reason or the IAWK12, IAWK24 and FPA.
- number and percentage of participants discontinuing treatment but continuing study assessments for the IAWK12, IAWK24 and FPA.
- number and percentage of participants who roll over to OLE study ARGX-113-2105 for the FAS, IAWK12, IAWK24 and FPA.

A listing of participant disposition will be prepared to present information about treatment allocation, treatment discontinuation and study discontinuation.

### 8.2. Protocol Deviations

- Frequency counts and percentages of participants with protocol deviations will be summarized, by class of deviations and overall using the FAS for the FPA.
- A listing will be prepared containing types of deviations and class along with additional information concerning all protocol deviations as available.

Document: BIOSdata\argenx\Efgartigimod\HAB40220\Biostatistics\Documentation\SAP

Author: Version Number: 3.0

Version Date: 02 May 2024

Template No.: CS\_TP\_BS016 Revision 7 Reference: CS\_WI\_BS005

Page 30 of 64

# 9. DEMOGRAPHIC AND OTHER BASELINE CHARACTERISTICS

Demographic and other baseline characteristics will be summarized using descriptive statistics for the FAS for IAWK12, IAWK24 and FPA.

The following demographic and other baseline characteristics will be reported for this study:

- Age (years) calculated relative to date of consent overall.
  - 18-<65 years
  - 65-<75 years
  - >=75 years
- Sex
  - Childbearing potential for female subjects only
- Race
- Ethnicity
- Base line weight (kg)
- Height (cm)
- Baseline BMI (kg/m²)
- Time since diagnosis (years) calculated relative to date of consent.
- SARS-CoV-2
- Active stand test (HR on 10-minute stand)
- Head-up tilt test

Summary statistics including n, mean, median, SD, Q1, Q3, minimum and maximum will be presented for continuous variables such as age, height, weight, BMI, time since diagnosis, active stand test (HR on 10-minute stand) and head-up tilt test. Frequency counts and percentages will be presented for categorical variables such as sex, race, ethnicity, and SARS-CoV-2.

All demographic data and baseline characteristics will be listed.

### 9.1.Derivations

- BMI  $(kg/m^2)$  = weight (kg)/ height  $(m)^2$
- Time since diagnosis is defined as (date of ICF date of diagnosis) / 365.25. Partially missing date of diagnosis will be imputed as follows:
  - Missing day of diagnosis will be imputed with 1

Document: BIOSdata\argenx\Efgartigimod\HAB40220\Biostatistics\Documentation\SAP

Author: Version Number: 3.0

Version Date: 02 May 2024

Template No.: CS\_TP\_BS016 Revision 7 Reference: CS\_WI\_BS005

• Percent reduction = (baseline-actual)\*100/baseline

### 10. MEDICAL HISTORY

Surgical and Medical History & Concomitant illnesses information will be presented for the SAF. Medical History and Concomitant illnesses will be coded using the latest version of MedDRA (medical dictionary for regulatory activities).

- Medical History conditions are defined as those conditions which stop prior to or at screening. Hence, any
  medical history abnormalities/conditions and any event including medical history for COVID and POTS
  before or at screening will be presented as Medical History.
- Concomitant illnesses which started prior to or at screening date and are ongoing during the study will be reported. These are also recorded in Medical History page of the eCRF.
- Medical history and concomitant illnesses will be presented by SOC and PT.

Details collected as a part of the medical history must include but are not limited to all previous treatment/therapy for COVID-19 and post—COVID-19 POTS.

Frequency and percentage of participants with findings by SOC and PT will be presented for FPA only.

# 11. THERAPIES

All therapies will be coded using WHO-DRUG and presented for the SAF. Anatomical Therapeutic Chemical (ATC) selection is performed. ATC coding up to level 4 is available in the clinical database.

See Appendix 3 for handling of partial and missing dates for medications

Based on their start dates, therapies will be allocated to 1 or both of the following categories:

- Prior therapy: the therapy strictly started before the first dose date.
- Concomitant therapy: the therapy was taken on or after the first dose date.

If the start and/or stop date is incomplete or missing, the therapy will be allocated to both categories unless the available parts of the start and/or stop date provide evidence that the therapy was not administered during the specific period.

Document: BIOSdata\argenx\Efgartigimod\HAB40220\Biostatistics\Documentation\SAP

Author: Version Number: 3.0

Version Date: 02 May 2024

Template No.: CS\_TP\_BS016 Revision 7 Reference: CS\_WI\_BS005

Page 32 of 64

• Prior and concomitant therapies will be tabulated by ATC class (level 1 and 3) and generic term. All prior and concomitant therapies will be listed.

### 12. STUDY MEDICATION EXPOSURE

Exposure to IMP in days will be summarized for the SAF for IAWK12, IAWK24 and FPA.

The infusion start date/time and infusion end date/time of each dose administered along with total dose administered at each visit will be recorded. The date of first study infusion will be taken from the eCRF "Exposure - Infusion" form. The date of last study infusion will be taken from the eCRF "End of Treatment" form. Interruptions, compliance, and dose changes are not taken into account for duration of exposure.

 As per protocol, a variation of more than 10% of the amount of 10 mg/kg will be considered an overdose. Overdosed information is as collected in "Exposure – Infusion" page of eCRF.

The total treatment administration duration will be summarized using descriptive statistics. All IMP administration data will be listed. Participants with an overdose of IMP will be listed.

### 12.1. Derivations

- Total treatment administration duration (days) = date of last IMP administration date of first IMP administration + 1.
- Number of administrations = Number and percentage of participants receiving 1,2,3 etc. administrations overall

### 13. STUDY MEDICATION COMPLIANCE

The infusion is given once a week by site staff or delegate. At least, the first 3 doses of IMP (at baseline, week 1 and 2 or subsequent if previous doses are missed) must be administered on-site.

The compliance will be summarized descriptively. Compliance will be further categorized as <80, 80-100, >100.

### 13.1. Derivations

Compliance is defined as: 100\* (number of doses received/number of doses expected). Number of doses

Document: BIOSdata\argenx\Efgartigimod\HAB40220\Biostatistics\Documentation\SAP

Author: Version Number: 3.0

Version Date: 02 May 2024

Template No.: CS\_TP\_BS016 Revision 7 Reference: CS\_WI\_BS005

Page 33 of 64

expected will be based on participants expecting study drug infusion/administration of eCRF page "Exposure – Infusion" irrespective of dosing received. Only visits up to treatment discontinuation are considered in the compliance calculation.

# 14. EFFICACY OUTCOMES

# 14.1. Primary Efficacy

### 14.1.1. Primary Efficacy Variables & Derivations

The primary efficacy variables are:

- Change from baseline to week 24 in the Composite Autonomic Symptom Score 31 (COMPASS 31)
- Change from baseline to week 24 in the Malmö POTS Symptom Score (MaPS)

Efficacy endpoints will be analyzed using the FAS for IAWK12 and IAWK24 (Note data will be used for all subjects up to the cut of date for IAWK12, the data will not be truncated to week 12 therefore the change from baseline to week 24 ANCOVA will contain a subset of the subjects available at week 12 cut off,, whereas the MMRM will contain all subjects within the cutoff regardless of where they are within the trial up to week 24.)

Estimand for primary analysis is as defined in Table B. The estimand is the difference between treatment arms in change from baseline to week 24 in COMPASS-31 and MaPS irrespective of stopping IMP or using prohibited medication. Missing data due to withdrawal of consent/loss to follow-up will be imputed based on subjects remaining in the study, irrespective of whether those subjects discontinued study treatment or used prohibited medications later than the imputation.

Intercurrent Events (ICE) are early discontinuation of study treatment and use of any prohibited medications.

# 14.1.1.1. Change from baseline to week 24 in the Composite Autonomic Symptom Score 31 (COMPASS 31) (2-week recall version)

The primary objective of the study is to evaluate the efficacy of efgartigimod in reducing the severity of post-COVID-19 POTS symptoms.

For change from baseline to week 24 in COMPASS 31 (2-week recall version) and MaPs, between treatment group difference will be analyzed using longitudinal mixed model repeated measures (MMRM). Without

Document: BIOSdata\argenx\Efgartigimod\HAB40220\Biostatistics\Documentation\SAP

Author: Version Number: 3.0

Version Date: 02 May 2024

Template No.: CS TP BS016 Revision 7 Reference: CS WI BS005

Effective Date: 01Nov2021

argenx Confidential 34

Page 34 of 64

imputation of intercurrent events.

The model will be implemented in SAS using the MIXED procedure and will include the change from baseline in COMPASS31 as the dependent variable and baseline value of COMPASS31, interaction of baseline value with visit as covariates. Fixed effects in the model will be treatment, visit and treatment by visit interactions. The visits included in the model will be weeks 2, 4, 12 and 24. All data will be included for subject in the IAWK12 even if it is for visits after week 12.

Within-subject correlation will be modeled by assuming an unstructured variance covariance matrix, and the Kenward-Roger degrees of freedom method will be used.

If the default Newton-Raphson algorithm used by SAS PROC MIXED fails to converge, the following steps will be taken to avoid lack of convergence while maintaining an unstructured variance:

The Fisher scoring algorithm (via the SCORING=5 option of the PROC MIXED statement) will be used to obtain the initial values of covariance parameters.

If the above fails, the no-diagonal factor analytic structure will be used, which effectively performs the Cholesky decomposition via the TYPE=FA0(V) option of the REPEATED statement, where V is the total number of distinct visits in the response vector (counting only rows where all model components are non-missing).

If all of the above fail, the variance-and-correlations parameterization will be attempted using TYPE=UNR.

In case if model does not converge after all of the above steps, following covariance structures will be tested for convergence (in order) ANTE(1), TOEPH, ARH(1), CSH, TOEP, AR(1), and CS.

To estimate the difference between the efgartigimod and placebo in mean change from baseline to Week 24, a treatment-by-visit interaction contrast will be constructed (i.e., the treatment group contrast at Week 24). On the basis of this analysis, LS means, SE with 95% CI for placebo and efgartigimod will be reported, along with difference in LS means of efgartigimod vs placebo (with SE), 95% 2-sided CI. 2-sided p-value for testing differences between treatment groups will also be presented. Inference will be based on the precision of the estimation rather than hypothesis testing.

Sample SAS code to be considered as below (SAS code is regarded as "draft" until fully validated at the analysis stage):

```
proc mixed data=COMPASS31 method=REML;
    class BCOMPASS31 ARMCD VISIT USUBJID;
    model change = BCOMPASS31 ARMCD VISIT BCOMPASS* VISIT
    ARMCD*VISIT/ddfm=kenwardroger;
    repeated VISIT / type=un subject = USUBJID;
    lsmeans ARMCD*VISIT / pdiff cl;
    ods output lsmeans = lsm; * contains the adjusted means;
    ods output diffs = dif; * contains treatment differences;
```

Document: BIOSdata\argenx\Efgartigimod\HAB40220\Biostatistics\Documentation\SAP

Author: Version Number: 3.0

Version Date: 02 May 2024

Template No.: CS\_TP\_BS016 Revision 7 Reference: CS\_WI\_BS005

Page 35 of 64

run;

For change from baseline to week 24 in MaPS, between treatment group difference will be analyzed using MMRM, except with change from baseline in MaPS as the dependent variable and baseline value of MaPS as covariate.

The visits included in the model will be weeks 2, 4, 8, 12, 18 and 24.

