### 14.1.1.3. Supplementary Analysis of Primary Efficacy Variables

COMPASS 31 questionnaire is to evaluate the severity and distribution of autonomic symptoms in various autonomic nerve disorders. The 31-item questionnaire addresses 6 domains: orthostatic intolerance, vasomotor, secretomotor, bladder, pupillomotor, and gastrointestinal-mixed upper and diarrhea. The original version of COMPASS 31 (longer recall) will be administered at screening and the modified version (2-week recall) will be administered at baseline and all other time points. The modified COMPASS 31 version used in the ARGX-113-2104 study modified the recall period to 2 weeks in contrast with the original COMPASS 31.

Document: BIOSdata\argenx\Efgartigimod\HAB40220\Biostatistics\Documentation\SAP

Author: Version Number: 3.0

Version Date: 02 May 2024

Template No.: CS\_TP\_BS016 Revision 7 Reference: CS\_WI\_BS005

Effective Date: 01Nov2021

argenx Confidential 36

Page 36 of 64

Participants are asked to respond to each of the item question using different, response options depending on each item, based on their perceived symptoms experience over the last 2 weeks. The response options are different depending on item content and vary from dichotomous to 7-point scale options. The modified COMPASS 31 has 6 domains that sum up to a total score of 0 to 100. Higher scores indicate a more severe degree of autonomic symptoms.

The modified COMPASS 31, scoring algorithm for each domain and total scores will be provided by external vendor. This total score will be considered for change from baseline analysis.

The supplementary primary efficacy analysis will be performed for the FAS for IAWK12 and IAWK24. Summary statistics will also be provided in terms of absolute value and changes from baseline for each visit where no imputation performed on missing data.

The estimand uses the composite approach, and is the difference between treatment arms in change from baseline to week 24 in COMPASS-31 and MaPS with outcomes after stopping IMP and /or using prohibited medication imputed as gaining no further benefit over and above that of the control arm.

Treatment Condition: Efgartigimod or placebo assuming less efficacious outcome post ICE Population: Randomized participants with post—COVID-19 postural orthostatic tachycardia syndrome as defined in FAS.

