RUN;

Merge ICEs patient wise

Apply MAR for Placebo treated patient with or without ICE it will be

PROC MI DATA=DIA\_mono\_(where=(trt=0)) NIMPUTE=1 SEED=4648 OUT=DIA\_imputed\_MAR;

by \_imputation\_;

VAR trt BASVAL change 1-change 4;

CLASS trt;

MONOTONE REGRESSION;

RUN;

Document: BIOSdata\argenx\Efgartigimod\HAB40220\Biostatistics\Documentation\SAP

Author: Version Number: 3.0

Version Date: 02 May 2024

Template No.: CS\_TP\_BS016 Revision 7 Reference: CS\_WI\_BS005

Page 38 of 64

Apply MNAR only for those ICE under treatment arm who have intercurrent event other than 'study treatment discontinuation'.

If the above methodology is unable to be undertaken due to the small sample sizes expected at week 12 analysis or subsequently at week 24, the ANCOVA analysis will be undertaken on observed data only, For the change from baseline to 24 weeks for both the COMPASS 31 analysis an ANCOVA will also be calculated using the FAS by the Proc Mixed procedure, example code is:

```
Ods output estimates =est;
proc mixed data=COMPASS31 method=REML;
class BCOMPASS31 ARMCD;
model change = BCOMPASS31 ARMCD /solution;
LSMEANS trt / diff=control('0') cl;
ODS OUTPUT Diffs=lsdiffs LSMeans=lsm solutionF=Parms;
BY visit _imputation_;
run;
(i.e using week 24 data only.)
```

Combine the imputations using proc MIanalysis

```
proc\ mianalyze\ parms (class var=full) = lsdiffs;
```

BY visit;

class trt;

modeleffects trt;

ods output ParameterEstimates=MIAN lsdiffs;

run;

Document: BIOSdata\argenx\Efgartigimod\HAB40220\Biostatistics\Documentation\SAP

Author: Version Number: 3.0

Version Date: 02 May 2024

Template No.: CS\_TP\_BS016 Revision 7 Reference: CS\_WI\_BS005

Effective Date: 01Nov2021

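### The draft SAS code lists baseline COMPASS 31 in CLASS, against the SAP text; run that way, it would fit one parameter per baseline score and widen the Week 24 interval

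*SAP*

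**What the plan says.** The prose of SAP 14.1.1.1 puts "baseline value of COMPASS31, interaction of baseline value with visit as covariates" in the MMRM and names treatment, visit and treatment-by-visit separately as fixed effects. Sections 14.1.1.2, 14.2.1.3 and 14.2.1.4 repeat the covariate role for MaPS and the two PROMIS scores. Neither document says that baseline is to be categorised.

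The code differs:

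- MMRM (14.1.1.1): "class BCOMPASS31 ARMCD VISIT USUBJID", followed by "model change = BCOMPASS31 ARMCD VISIT BCOMPASS* VISIT". The interaction uses BCOMPASS, a name defined nowhere.
- ANCOVA (14.1.1.3): "class BCOMPASS31 ARMCD". The model term for treatment is ARMCD, but the next step is "LSMEANS trt / diff=control('0') cl", and the MIANALYZE step also uses trt.

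Section 14.1.1.1 calls its code draft until validated, and 14.1.1.3 permits small changes. Section 14.1.1.1 also states that "LS means, SE with 95% CI for placebo and efgartigimod will be reported", together with the difference and its interval, and that inference rests on the precision of the estimate. At the Week 12 interim, section 14.1.1 says "the change from baseline to week 24 ANCOVA will contain a subset of the subjects available at week 12 cut off".

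**The concern.** A variable in CLASS is fitted as a factor. With 42 participants and a score running from 0 to 100, most baseline values occur once or twice, so the model spends a parameter on nearly every one. In the ANCOVA, a score seen in only one arm then says nothing about the treatment difference. The same holds in the MMRM if the interaction is renamed BCOMPASS31*VISIT and CLASS is left alone.

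What is at stake is precision, which the SAP makes the basis of inference. Both blocks need editing before they can run, because of the BCOMPASS and trt/ARMCD names. The obvious edit repairs the names and leaves CLASS in place. With whole-point scores the ANCOVA would then print an ordinary-looking but much wider interval. These are the only blocks that fit the COMPASS 31 treatment comparison. For the COMPASS 31 ANCOVA, the code is also the only explicit model statement: section 14.1.1.2 refers its ANCOVA to 14.1.1.1, which presents only the MMRM.

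**Working it through.** **Inputs.** Protocol 9.5: SD 15, mean 50, correlation 0.8 (trailing digits read as citation numbers). Protocol 1.1 and 6.3: about 42 participants, 2:1, so 28 and 14. The SAP does not give the step between possible scores ("scoring algorithm for each domain and total scores will be provided by external vendor"), so whole points are assumed first. Results are shown without and with a floor of 35 on baseline: protocol 5.1 applies 35 only at screening, and SAP 6.3 keeps the original-version assessment used there out of baseline.

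**The plan's own figure.** The planned half-width is blacked out and cannot be matched. From the visible inputs, the SD of change is 15 × √(2 × 0.2) = 9.49, and the half-width is 1.96 × 9.49 × √(1/28 + 1/14) = 6.09.

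**Baseline continuous (the prose).** Residual SD = 15 × √(1 − 0.8²) = 9.0. Information on the difference is about 28 × 14/42 = 9.33, so the SE is about 9/√9.33 = 2.95. Residual df = 42 − 3 = 39. The simulated median half-width is 6.0.

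**Baseline in CLASS (the ANCOVA code).** Information = the sum over scores of n1 × n0/(n1 + n0). A score held by two efgartigimod and one placebo participant adds 2 × 1/3 = 0.67; a score held in one arm only adds 0. Residual df = 42 − levels − 1. Medians over 6,000 simulated trials per setting:

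| | No floor | Floor 35 |
|---|---|---|
| Distinct scores | 30 | 27 |
| Residual df | 11 | 14 |
| Sharing a score with the other arm | 29% | 36% |
| SE ratio | 1.81 | 1.62 |
| CI width ratio | 1.97 | 1.72 |
| Half-width | 11.9 | 10.4 |

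The ratios agree with each other. The t quantiles are 2.201 (11 df), 2.145 (14 df) and 2.023 (39 df), so 1.81 × 2.201/2.023 = 1.97 and 1.62 × 2.145/2.023 = 1.72. A separate 2,000-trial simulation that also estimated the residual variance gave half-widths of 11.6 and 10.3.

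**Finer scores.** At 0.5-point steps the ANCOVA interval was 2.3 to 2.9 times as wide across runs. At 0.1 steps an interval exists in only 37% (no floor) and 50% (floor) of trials, and at 0.01 steps in about 1%. An interval needs at least one score found in both arms and at least 1 residual df.

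**MMRM.** Four visits, generalised least squares with known covariance (residual variance 225 − 0.64 × 225 = 81, between-visit covariance 180 − 144 = 36). Median Week 24 SE ratio with complete data, no floor and floor:

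- BCOMPASS read as a numeric copy of baseline: 1.53 and 1.40. Participants with unshared scores still contribute.
- Interaction renamed BCOMPASS31*VISIT with CLASS kept: 1.81 and 1.63.

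At assumed dropout of 5 to 20%, the difference stays estimable in at least 98% of trials, with SE ratios of 1.4–1.5 and 1.6–1.9. The required Week 24 arm LS means fare worse. Under the numeric-copy reading they are non-estimable in at least 94% of trials even with complete data. Under the classed interaction the share is 0% with complete data, 58–64% at 5% dropout, 80–86% at 10% and 98–99% at 20%.

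**Week 12 interim ANCOVA.** The subset size is not given. Assuming 20:10 and whole points, the interval is 2.1 to 2.5 times as wide. At 14:7 it is 2.9 to 3.9 times as wide where it exists, and about 11 to 20% of trials have none.

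**The case against.** The best defence is that the specification is correct and only illustrative code is wrong. The MMRM code is labelled draft until validated, minor alterations are allowed, and the prose says covariate throughout, including for MaPS and PROMIS. The SAP's own PROC MI steps carry baseline as BASVAL outside CLASS, so it is numeric there. Harm requires a programmer to repair the names and a validator to miss the CLASS entry. All of this stands. It makes the issue minor and shows a slip rather than an intended model.

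The size is also open to challenge. The score step, interim subset sizes and dropout rates are assumptions, and reading BCOMPASS as a numeric copy is only one possible repair. The CI-width ratios are for the supplementary ANCOVA. For the primary MMRM only SE ratios were obtained, with known covariance rather than the specified unstructured matrix with Kenward-Roger df. These limits stand too.

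Detection is partly on the sponsor's side: non-estimable arm LS means, or a missing interval with fine scores, would be noticed. But in the MMRM the difference and its interval would still print, and with whole-point scores the ANCOVA gives no warning. None of this removes the contradiction between text and code in both blocks.

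**Conclusion.** The concern holds, as a minor one. The text and both code blocks disagree on the role of baseline, and the code's version loses precision in the Week 24 contrast. With 28:14, complete data, the protocol's SD and correlation, and assumed whole-point scores, the ANCOVA interval becomes 1.7 to 2.0 times as wide and the MMRM standard error 1.4 to 1.8 times as large. Finer scores make the ANCOVA loss worse, up to having no interval at all. No bias in the treatment estimate is claimed. No figure is given for MaPS, because SAP 14.1.1.2 describes 11-point items and protocol 8.2.1.2 a visual analog scale, which leaves the score step unclear.

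**What to change.** Make the code match the prose:

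1. Delete BCOMPASS31 from the CLASS statements in SAP 14.1.1.1 and 14.1.1.3, so that baseline is continuous.
2. Write the MMRM interaction as BCOMPASS31*VISIT.
3. Use one treatment variable name through the ANCOVA, LSMEANS and MIANALYZE steps, and state how BASVAL in the imputation code maps to BCOMPASS31.
4. Carry the corrected template to the MaPS and PROMIS models.

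This changes a few words in the SAP code before the analysis is run. It needs no new data, has no operational cost and does not alter the specified model.
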